B.6. Patient Withdrawal

A patient has the right to withdraw from the study at any time, for any reason, and without repercussion. The investigator has the right to withdraw a patient from the study in the event of an intercurrent illness, adverse event, treatment failure, protocol violation, cure, and for administrative or other reasons. An excessive rate of withdrawals would render the study uninterpretable; therefore, unnecessary withdrawal of patients will be avoided. Should a patient (or a patient's legally authorized guardian or representative) decide to withdraw, all efforts will be made to complete and report observations as thoroughly as possible. Early termination procedures will be followed.

B.7. Patient Replacement

Patients prematurely withdrawn from the study can be replaced, if needed, to ensure an adequate number of evaluable patients. The investigator, (in cooperation with the study statistician, if applicable) will decide whether or not to replace withdrawn patients.

B.8. Investigation Drug Management

At each study site, the drug management will be performed by their respective Investigational Drug Services (IDS). Study drug will be refrigerated at the site at a temperature of 2 to 8°C; refrigerator temperature will be logged daily. At no time, will product be left unattended or outside the control of an individual knowledgeable with regard to product temperature requirements. Moreover, no one will administer product that has not been maintained according to temperature requirements. Study drug will be shipped at a temperature of 2 to 8°C to the investigator or designee at regular intervals or as needed during the study. During site close-out, and following drug reconciliation and documentation, all opened and unopened vials of study drug will be kept current. The primary investigator will account for all opened and unopened vials of study drug. These records will contain the dates, quantity, and study medication:

- a) dispensed to each patient,
- b) returned from each patient (if applicable), and
- c) disposed of at the site or returned to Amgen Inc. or designee

All accountability records will be made available for inspection by regulatory agency inspectors.

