We power our study on the primary endpoint of change in stenosis and PAV. The GLAGOV trial showed 0.95% reduction in PAV for patients randomized to Repatha versus a 0.05% increase in PAV for patients in the placebo arm and was 78 weeks in length. Because the major intracranial arteries have a similar luminal diameter to coronary arteries, we may reasonably expect a 1% reduction in PAV for our 78 week study as documented in previous literature. Patients with intracranial atherosclerosis can be expected to have at least 3 additional sites of atherosclerosis, including extracranial arteries, that will be included in the series of PAV outcomes. Each subject will provide four sites of atherosclerosis and therefore, 4 PAV measurements. This cluster designed study will be modeled by a mixed effects linear regression to account for the cluster of arteries per patient. We obtain >80% power for our sample size of 150 patients, two-sided significance level 0.05, and a conservative assumed standard deviation of 4% from previous studies for the assumed 1% reduction in PAV against the documented control PAV of 0%.²³ With 150 patients, the minimum effect size possible to detect with 80% power is a 0.51% reduction. A 0.50% difference has been reported to be the cutoff to distinguish individuals that experience cardiovascular events versus those who do not.²³ Assuming a withdrawal rate of 25-30%, we would still reach >90% power for a 1% reduction with the above-listed conditions. We do not expect to show a significant reduction in recurrent stroke, but anticipate seeing a trend towards that outcome. This data could be used to accurately construct and power a subsequent trial with the primary outcome of recurrent stroke. Finally, in GLAGOV the linear relationship between change in stenosis, PAV and on-treatment LDL-C was very robust. We will be replicate this finding through means of a generalized linear mixed effects model. Our effective sample size may be sufficiently large enough to match the GLAGOV trial as each patient will be able to contribute an average of 4 arteries giving us an expected sample size between 800 and 1200 dependent on a conservative prediction of intra-class correlation. All reported p-values will be twosided and deemed significant at the 0.05 level.

D.3. Loss to Follow-up

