Based on the SPRINT MIND trial, we anticipate that up to 25-30% will not complete the follow-up clinic visit or vwMRI, and have accounted for this in our sample size calculation.³¹ If less patients than expected return for yearly follow-up MRI scans, we can enroll additional patients as needed, but do not expect this to be necessary or costly if necessary. If we have difficulty finding enough patients to enroll in the study, we will expand enrollment to the VA hospitals at our study sites, which would significantly increase potential patients.

E. Safety Definitions, Reporting, and Monitoring

E.1. Adverse Event (AE)

An AE is any untoward medical occurrence in a patient administered the study drug which may or may not have a causal relationship with the study drug. Therefore, an AE is any unfavorable and

unintended sign (including abnormal laboratory finding), symptom, or disease which is temporally associated with the use of a study drug, whether or not considered related to the study drug. An AE also includes any worsening (i.e. any clinically significant change in frequency and/or intensity) of a pre-existing condition that is temporally associated with the use of the study drug. The most commonly occurring adverse reactions reported from clinical studies with Repatha were injection site reactions (including erythema/redness, itching, swelling, pain, tenderness), upper respiratory tract signs and symptoms (mainly nasopharyngitis, sinusitis, influenza, and upper respiratory tract infection), back pain, urinary tract infection, and cough. For this study, investigators will record all potential AEs, but the following are always considered as AEs:

- a) Increase in ALT: ALT >3 x ULN
- b) Allergic events: allergic drug reactions and/or local injection site reactions deemed to be allergic by the Investigator (or have an allergic component), that require consultation with another physician for further evaluation of hypersensitivity/allergy as per the Investigator's medical judgment should be reported as an AE.

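### Withdrawal from follow-up for possibly outcome-related reasons, with discretionary replacement, can bias the single-arm change from 0%, more likely but not certainly towards regression

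*Combined protocol and SAP*

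**What the plan says.** Section B.6 (Patient Withdrawal) allows investigators to take someone out of the trial. The grounds listed are: "in the event of an intercurrent illness, adverse event, treatment failure, protocol violation, cure, and for administrative or other reasons". The wording concerns leaving the study, not only stopping the drug; reasons for permanently stopping the drug are listed separately in E.8. B.6 also promises that "all efforts will be made to complete and report observations as thoroughly as possible", but that sentence is about withdrawal decided by the patient or a representative. The early termination procedures it mentions are not described.

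Section B.7 (Patient Replacement) states: "Patients prematurely withdrawn from the study can be replaced, if needed, to ensure an adequate number of evaluable patients". On who decides: "The investigator, (in cooperation with the study statistician, if applicable) will decide whether or not to replace withdrawn patients". No trigger, cap or timing is given, and neither evaluable nor treatment failure is defined.

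The schedule in B.9 (Figure 1) has vessel wall MRI at Day 1 and Day 546 only. Both primary endpoints in C.1 need the second scan. D.1 compares the change with an assumed 0%. D.2 claims more than 90% power after 25-30% withdrawal. D.3 says of the same loss that the authors "have accounted for this in our sample size calculation", and adds that more patients can be enrolled if fewer than expected return for MRI.

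**The concern.** A patient withdrawn before week 78 has no primary endpoint value. Some of the listed reasons may be related to how the disease is progressing. In a randomised trial a control arm might share some of that selection. Here the comparator is a fixed number, so any difference between those who leave and those who stay passes straight into the estimate and its test.

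The plan does not say who is in the primary analysis or how missing scans are handled. In practice the estimate would rest on patients with both scans. Replacement then restores the count of such patients without restoring the information lost. The study is meant to lay the foundation for a randomised trial (A.5), so a distorted effect would carry into the planning of that trial.

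**Working it through.** **1. The plan's own figures.** Inputs from D.2: 150 patients, four sites each, SD 4 points, two-sided 0.05, effect 1 point against 0. The intra-class correlation (ICC, ρ) is not stated. With n_eff = 4n/(1 + 3ρ), power = Φ(δ√n_eff/SD − 1.96).

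- At ρ = 1, n_eff = 150 and power = Φ(√150/4 − 1.96) = Φ(1.10) = 86.5%. The claim of more than 80% holds even in this worst case.
- A minimum detectable effect of 0.51 needs n_eff = [(1.960 + 0.842) × 4/0.51]² ≈ 483. Then 600/483 = 1.243, so ρ ≈ 0.081.
- Power of 90% for 1 point needs n_eff = [(1.960 + 1.282) × 4]² ≈ 168. With 25% lost (112.5 patients), 450/168 = 2.68, so ρ may be up to about 0.56. With 30% lost (105 patients), 420/168 = 2.50, so up to about 0.50. At ρ = 1, power is 75% with 112 patients and 73% with 105.

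So the allowance for 25-30% loss supports the stated power unless the ICC is high.

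**2. Bias from losing the week-78 data.** Let w be the share withdrawn, C the completers' mean change and D the withdrawn patients' mean change. The all-enrolled mean is (1 − w)C + wD, and a completers-only estimate overstates regression by w(D − C). Take C = -1.0, the effect assumed in D.2. D is an assumption, because the documents do not give it.

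| Assumed D | w = 5% | w = 10% | w = 25% | w = 30% |
|---|---|---|---|---|
| 0 (the plan's untreated value) | overstated 0.05 | 0.10 | 0.25 | 0.30 |
| -0.5 | overstated 0.025 | 0.05 | 0.125 | 0.15 |
| -1.0 (same as completers) | 0 | 0 | 0 | 0 |
| -2.0 | understated 0.05 | 0.10 | 0.25 | 0.30 |

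For example, with D = 0 the all-enrolled mean is -0.75 × 1.0 = -0.75 at 25% and -0.70 at 30%.

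**3. What replacement adds.** The formula in step 2 has no replacement term. If replacements leave in the same way, the completers' mean stays at C and only the standard error, 4/√n_eff, shrinks. To see the consequence, assume a true all-enrolled mean of 0, 30% withdrawn, and withdrawn patients 1 point worse than completers. Then C = -0.30 and D = +0.70 (0.7 × -0.30 + 0.3 × 0.70 = 0). The chance of falsely declaring regression, nominally 2.5%, is Φ(0.30/SE − 1.96):

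| ICC | 105 completers, no replacement | 150 completers, with replacement |
|---|---|---|
| 0.081 | SE 0.218, 28% | SE 0.182, 38% |
| 1 | SE 0.390, 12% | SE 0.327, 15% |

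Most of the excess error is there without replacement. Replacement adds to it.

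**The case against.** Several stronger readings are tempting, and the documents do not support them.

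- **That replacement creates the bias.** It does not. The figures in step 2 are the same with or without B.7, so deleting B.7 alone would leave them unchanged. Nor does the plan state a completers-only analysis; that follows from its silence.
- **That regression is certainly overstated.** Cure is on the same list as treatment failure and would act the other way. Administrative reasons and protocol violations may be unrelated to plaque.
- **That investigators would remove poor imaging results.** There is no interim vessel wall MRI, scheduled lipid tests are only at baseline and Day 546, and C.1.a has the neuroradiologists read scans once enrolment is complete. Selection on PAV or stenosis could only be indirect, for example through clinical events or unscheduled tests.
- **That the bias is 0.5-0.6 points, as large as the detectable effect of 0.51.** This needs withdrawn patients to progress by +1 point: 0.25 × 2 = 0.50 and 0.30 × 2 = 0.60. Nothing in the documents supports +1. The placebo change quoted in D.2 is +0.05%, and the plan's untreated value is 0.
- **That replacement is never needed for power.** This depends on an ICC that the plan does not give. B.7 is conditional, and D.3 does not expect extra enrolment to be necessary. Both can be read as contingencies for loss beyond the allowance.

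It is also fair that the 25-30% in D.3 is all non-completion of the final visit or scan, not a rate of withdrawal for treatment failure. B.6 says unnecessary withdrawals will be avoided, and B.7 foresees some role for the statistician. B.10 estimates 2 years from first patient enrolled to last patient out. After 78 weeks of treatment this leaves about 104 − 78 = 26 weeks for enrolment, so late withdrawals could hardly be replaced by patients who complete.

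These points limit the size and certainty of the concern. They do not answer it. The effort promised in B.6 does not expressly cover withdrawal by the investigator. The mixed model in D.1 does not help by itself: a patient without the second scan has no change value at any site.

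**Conclusion.** The concern holds in a limited form. B.6 permits loss of the primary endpoint for reasons that may be related to outcome, and neither a control arm nor a stated analysis set or missing-data method protects the estimate. The result can be biased, more likely but not certainly towards regression. Replacement under B.7 is an aggravating factor: it hides attrition and tightens the interval around a biased mean.

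The plausible size depends on how many are lost and how they fare. It is small (0.05-0.10 points) at 5-10% withdrawn and material (0.25-0.30 points against an expected 1 point) at 25-30%, if completers average -1.0 and withdrawn patients average 0. The error rates in step 3 rest on an assumed 1-point difference between the groups and on an ICC either inferred from the 0.51 figure or set to its extreme. The documents supply neither the outcomes of withdrawn patients nor the ICC.

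**What to change.** 1. In B.6, separate stopping study drug from leaving study follow-up, so that treatment failure, adverse event or cure does not by itself end follow-up. This does not touch the criteria for stopping the drug.
2. Seek the already scheduled week-78 vessel wall MRI from every enrolled patient who has not withdrawn consent, whether or not still on drug.
3. Define the primary analysis set as all enrolled patients who received at least one dose. State a missing-data method, and a sensitivity analysis that sets patients without a week-78 scan to 0% change or worse.
4. Remove replacement from B.7. Otherwise, keep the replaced patients in the analysis set, report the number and reasons, and define evaluable and treatment failure.
5. Reconcile B.7 and D.3 with the 25-30% loss already allowed for in D.2, and state the ICC behind that allowance.

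The cost is protocol wording, some week-78 scans in patients off drug, and a possibly less favourable estimate.

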culprit lesions.²² The combination of stenosis + atheroma burden + luminal area produced an odds ratio of 3.99 (95% CI: 1.74-9.13, p=0.001) for culprit plaque. The GLAGOV study showed that PCKS9 inhibition reduced the percent atheroma volume of coronary arteries over a 78 week treatment period.²³ With atheroma volume now established as a viable biomarker, vwMRI is the optimal test to monitor it and stenosis, both for ICAD and in other locations of the cerebrovasculature, such as the carotid arteries, cervical vertebral arteries, and aortic arch.

A.5. Impact

The result of this study will be a dataset that lays the foundation for a randomized controlled trial of Repatha in ICAD patients. The data collected in this study will allow us to optimize a future clinical trial designed to demonstrate a reduction in stroke risk, ultimately making more efficient and economical progress towards our ultimate research goal of preventing stroke with Repatha. While we are proposing future studies to reduce ICAD stroke risk, it should be noted that our study will also evaluate the potential for Repatha to decrease cerebrovasculature stenosis and plaque burden, which would be a compelling primary prevention indication.

B. Approach

B.1. Study Hypothesis

We hypothesize that inhibition of PCSK9 with Repatha in patients with moderate to severe intracranial atherosclerosis will reduce validated biomarkers of stroke risk (stenosis and percent atheroma volume). To answer our hypothesis, we propose a single arm study of Repatha in 150 patients with a prior history of ischemic stroke and ICAD causing at least 50% stenosis of a major intracranial artery in the Circle of Willis ("index artery").

B.2. Study Design

We will enroll 150 ICAD patients with a prior history of ischemic stroke. Patients will be enrolled at up to 8 medical centers in North America. All patients will receive Repatha for 78 weeks and will have an MRI before beginning study medication and a comparison MRI immediately after completing study medication.

B.3. Investigational Treatment

The investigational treatment is Repatha 140 mg administered subcutaneously with a single-dose pre-filled pen syringe every 2 weeks for a total of 39 treatments. Dose modification is not allowed.

B.3.a. Inclusion Criteria

- Adult patients, ≥ 18 years of age

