All drug compliance records will be kept current and will be made available for inspection by regulatory agency inspectors. Study drug will be given to patient at the baseline visit, and preferably at 6 month intervals thereafter. Instructions for shipping study drug to patients are provided in the appendix.

B.9. Study Timeline

There are two in-person study visits (baseline and 78 week follow-up) when patients will undergo vwMRI, approximately 60 minutes long, with a simultaneous clinical evaluation by a study investigator physician and blood draw. Every 2-4 months, the study coordinator will determine medication adherence, adverse events, or patient-reported recurrent stroke (see **Figure 1**).

	Screen/ Baseline	Day 1	Day 60	Day 120	Day 180	Day 240	Day 320	Day 480	Day 546
Informed Consent	Х								
Medical History/Current medications	х		х	х	х	Х	х	х	х
Vitals	Х								Х
Review CTA or MRA ¹	х								
Vessel wall MRI		Х							Х
Pregnancy test	Х								
Creatinine	Х								Х
Lipid panel	Х								Х
Lipoprotein (a)	Х								Х
Apolipoprotein B	Х								Х
Physical exam	Х								Х
Neurological exam	Х								х
NIHSS	Х								Х
Modified Rankin Scale	х								Х
Stroke adjudication			Х	Х	Х	Х	Х	Х	Х
Adverse event determination			х	Х	х	Х	х	х	х
Serious adverse events			Х	Х	Х	Х	Х	Х	Х

Figure 1: Schedule of Activities

1. To confirm ICAD of a major intracranial artery

B.10. Study Duration

- Estimated duration of research (study start to final study deliverable): 2 Years / 6 Months
- Estimated duration of first patient enrolled to last patient out: 2 Year / 0 Months
- Estimated duration for Amgen to supply study drug: 2 Year / 0 Months

C. Study Endpoints

C.1. Primary Endpoints

The primary endpoints are nominal change in the stenosis and percent atheroma volume (PAV) of cerebrovasculture arteries from baseline to week 78. We will use measure stenosis and PAV on vessel wall MRI (vwMRI), which evaluates all arteries from the aortic arch to the distal intracranial vasculature in a single scan. The primary endpoints will be analyzed for both: 1) all intra- or extracranial arteries that have at least 25% stenosis, and 2) seperately for the intracranial arteries. Stenosis and PAV will be measured using standard methodology.

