
C.2.a. Secondary endpoint 1 measurement:

a) ICAD post-contrast plaque enhancement (PPE): is a dichotomous variable evaluated on the T1 pre- and post-gadolinium sequences, with multiplanar reconstruction so the ICAD can be seen in cross section.²⁶ PPE is defined by placing a region-of-interest over areas of gadolinium enhancement in ICAD to evaluate if it is equal to or exceeds the signal intensity of the pituitary infundibulum, as previously described.²⁷

- b) Carotid intraplaque hemorrhage (IPH): MPRAGE positive plaque is defined as voxels with at least 2-fold signal intensity compared to sternocleidomastoid muscle as previously described. MPRAGE positive plaques can be reliably identified. Kappa values for inter- and intra-rater reliability for detection of MPRAGE positive plaque were 0.806 and 0.818 respectively (very good agreement).^{28,29}
- c) MRA Flow Dynamics (**MFD**): We will measure MFD using accepted quantitative MRA methodology. The VERiTAS study provided prospective confirmation of the importance of MFD as a biomarker of stroke risk for patients with ICAD. Given that MFD can easily be measured in our vwMRI protocol, we will acquire the data required for its quantification.

C.3. Secondary endpoint 2

To better understand the mechanism of Repatha's effect on intra- and extracranial atherosclerosis, we will measure the endpoint of change in cholesterol markers [LDL-C, HDL-C, lipoprotein (a), apolipoprotein B, and triglyceride level]. The change in cholesterol markers will be correlated with the primary and secondary study endpoints on vwMRI. Cholesterol values will be measured at the baseline and comparison MRIs, which are 78 weeks apart. If standard of care lab values are available within 30 days of the study visit, they can be used in place of the study lab value. An additional exploratory outcome that we will measure is the composite endpoint of "recurrent stroke," which encompasses new patient-reported symptomatic ischemic stroke, transient ischemic attack, or asymptomatic strokes that emerge between MRIs.

C.3.a. Secondary endpoint 2 measurement:

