We will fit a mixed effects linear regression model, specifically a LOESS smoothing curve, to change in stenosis/PAV and on-treatment LDL-C, HDL-C, and lipoprotein(a). We will also use a multivariable linear regression model with the outcome of the primary endpoints, adjusted for covariates that could be confounders such as age, gender, smoking, statin use/dose and relevant medical comorbidities. The primary endpoints will also be compared to an assumed value of 0% change in stenosis and PAV that would correspond to optimal medical management without a PCSK9 inhibitor. Although, some studies have suggested statin therapy can reduce carotid atherosclerosis, no such effect is known for ICAD. For this analysis, we will use linear mixed effects model to detect differences in the stenosis and PAV endpoints between patients taking Repatha or the presumed historical control values of 0% change. For the secondary endpoints, we will use logistic and linear regression depending on the nature of the variable and use the primary predictors of on-treatment LDL-C, HDL-C, and lipoprotein(a). For the exploratory endpoint of recurrent stroke, we will use the above mentioned methods as well as a Cox proportional hazards model for the endpoint of recurrent stroke with the observed rate in this study compared to controls matched according to degree to stenosis of the index artery. Due to differences in arterial structure and flow dynamics, there may be a more significant plaque reduction in certain intracranial vessels. We anticipate subgroup analyses, for example comparing change in stenosis or PAV in the middle cerebral artery versus the vertebral artery.

D.2. Power Analysis

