- b) **Moderate:** Produces some impairment of functioning but is not hazardous to health. It is uncomfortable or an embarrassment. Treatment for symptom may be needed.
- c) **Severe:** Produces significant impairment of functioning or incapacitation and is a definite hazard to the patient's health. Treatment for symptom may be given and/or patient hospitalized.

If a laboratory value is considered an AE, its severity will be based on the degree of physiological impairment the value indicates.

E.7. Evaluation of Causality

The relationship to treatment will be determined by the investigator and reported on the CRF/eCRF and/or SAE form, as appropriate. Events related to atherosclerosis such as primary atherosclerosis complications, will be considered anticipated unless they are fatal or present with unusual features in the context of the underlying condition. When determining causality of such events, the sponsor will consider them in the context of that individual patient's condition. Events that may be considered anticipated in a patient with advanced disease may not be considered anticipated in a patient with milder disease.

The following terms will be used:

- a) Not Related: likely or clearly due to causes other than the study drug.
- b) **Related:** possibly, probably, or definitely related to the study drug.

E.8. Reasons for Permanent Discontinuation of Study Drug

When attributed to Repatha administration: hypersensitivity or angioedema reactions requiring hospitalization.

E.9. Investigator Alert notification

UCLA or its designee will inform all investigators participating in this clinical trial, as well as any other clinical trial using the same investigational drug, of any SAE that meets the relevant requirements for expedited reporting (an AE that is serious, unexpected based on the Investigator's Brochure, and has a reasonable suspected causal relationship to the study drug).

E.10. Premature Termination

The investigator will notify UCLA of a desire to close-out a site in writing, providing at least 30 days' notice. The final decision will be made by the investigator after consultation with UCLA. In all cases, the appropriate IRB and Health Authorities will be informed according to applicable regulatory requirements, and adequate consideration will be given to the protection of the patients' interests.

E.11. Monitoring of Study Site

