APPENDIX: Drug Shipment to Patients

- 1. When study medication is given to the coordinator, the hand packaging and labeling process will begin.
- 2. Study drugs need to be kept in a temperature range of 68°F to 77°F at all times, so to ship study medications we must prepare them with adequate ice packs and a Styrofoam box.
- 3. You can purchase the Styrofoam box and Ice Gel Pack on Amazon, which have the picture below and are very inexpensive.

- 4. Please ensure you keep the ice pack in a 68°F to 77°F temperature location at least 24 hours prior to shipment of drug.
- 5. Once the packaging is completed, prior to sending it to Fedex or UPS please ensure "UN3373 Biological Substance Category B" Labels/Stickers are attached on the box.
- 6. Once shipment is ready, you may contact UPS or Fedex via the internal mail office within institute. Please be sure that your shipment is by over-night shipping.
- 7. Once the study drugs are delivered to the participant, the study coordinator is required to contact participants to ensure study drugs were received and are not damaged.

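### Figure 1 schedules no adverse-event or stroke check for 160 days (Day 320 to Day 480), about 38 days beyond the four-month maximum in B.9

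*Combined protocol and SAP*

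**What the plan says.** B.9 provides two in-person visits, at baseline and at 78 weeks. Between them it relies on coordinator contacts: "Every 2-4 months, the study coordinator will determine medication adherence, adverse events, or patient-reported recurrent stroke". The sentence points to the table headed "Figure 1: Schedule of Activities" for the detail.

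After Day 1 that table has columns for Days 60, 120, 180, 240, 320, 480 and 546. The rows for stroke adjudication, adverse events and serious adverse events are marked in all seven. Adherence has no row of its own; the medical history and current medications row is marked in the same seven columns.

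Treatment runs throughout this period. Under B.3 the patient receives an injection "every 2 weeks for a total of 39 treatments", and A.3 describes it as self-administered. On resupply, B.8 says: "Study drug will be given to patient at the baseline visit, and preferably at 6 month intervals thereafter". Where drug is shipped, the Appendix adds that "the study coordinator is required to contact participants to ensure study drugs were received and are not damaged".

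C.3 defines recurrent stroke, an exploratory outcome, as "new patient-reported symptomatic ischemic stroke, transient ischemic attack, or asymptomatic strokes that emerge between MRIs". D.1 plans "a Cox proportional hazards model for the endpoint of recurrent stroke".

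**The concern.** The text and the schedule it cites disagree on how often patients are asked about adverse events and stroke. A site working from Figure 1 alone would leave a patient without a scheduled check for longer than B.9 allows. A site working from B.9 would add a contact, so ascertainment could differ between sites.

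Two things are at stake. The first is timeliness of safety information. The reporting times in E.3, and the E.5 rule to stop drug once pregnancy is confirmed, can operate only after the site knows of the event. Between the two visits these contacts are the only scheduled safety checks. The second is the recurrent-stroke outcome. A TIA that never reached care may leave no trace on MRI or in the records, so its capture and its date depend on what the patient recalls at the next contact. The outcome is exploratory, but D.2 says these data could help construct and power a later trial with recurrent stroke as the primary outcome, so event dates have some value.

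**Working it through.** **Inputs.** Contact days from Figure 1: 1, 60, 120, 180, 240, 320, 480, 546. Interval rule from B.9: at most four months. Treatment from B.3: 39 doses, two weeks apart. The last column agrees with the stated treatment length: 78 × 7 = 546 and 39 × 14 = 546.

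**Is a column missing from the extracted table?** It appears not. There are seven headers after Day 1 and seven marks in each of the three rows.

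**Intervals.** Successive differences are 59, 60, 60, 60, 80, 160 and 66 days, which sum to 545. Every interval but one is 80 days or less.

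**Against the B.9 limit.** At 30.4375 days per month, four months is 4 × 30.4375 = 121.75 days.
- 160 / 30.4375 = 5.26 months.
- Excess: 160 − 121.75 = 38.25 days. With 30- or 31-day months the limit is 120 or 124 days and the excess is 40 or 36 days.

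**Extent of the interval.** 160 / 545 = 29% of follow-up. If dose 1 is on Day 1, dose days are 1 + 14k. Those after Day 320 and up to Day 480 run from Day 323 (k = 23) to Day 477 (k = 34), which is 12 of the 39 doses. Most of this interval is allowed by B.9; only the last 38 days are not.

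**Waiting time.** The documents give no event rates. Assume events are spread evenly over the 545 days and surface only at the next scheduled contact. An event waits more than four months only if it falls in the first 38.25 days after Day 320. The share is 38.25 / 545 = 7.0% (6.6% to 7.3% for limits of 124 to 120 days). The mean wait is the sum of squared intervals divided by (2 × 545):

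| Schedule | Sum of squares | Mean wait (days) | Longest interval (days) |
|---|---|---|---|
| As printed | 50,637 | 46.5 | 160 |
| Day 400 added | 37,837 | 34.7 | 80 |
| Day 480 moved to Day 430 | 46,237 | 42.4 | 116 |

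**Where the last interim contact could go.** With no extra contact, a day X complies if X − 320 ≤ 121.75 and 546 − X ≤ 121.75, so X lies between Day 425 and Day 441. Day 430 gives 110 and 116 days.

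**Could 480 be a misprint?** If Day 400 was meant, the gap moves to Day 400–546, which is 146 days and still too long. If a day near 430 was meant, the schedule would comply. The documents do not settle this.

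**The case against.** A reader might infer that no site can satisfy both B.9 and Figure 1. That goes too far. Figure 1 forbids no extra contacts, and one additional call between Day 320 and Day 480 meets both. The B.9 interval also reads as approximate: the 59- and 60-day steps fall slightly short of two months at 60.9 days. That looseness does not stretch to 38 days at the upper end.

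A reader might also infer that nothing is learned of the patient for 160 days. The documents do not support that either. E.1 has investigators record all potential adverse events, and its overdose item expects some to be volunteered by patients. Hospitalised events will often be known sooner, and the only reasons listed in E.8 for permanent discontinuation are reactions that need hospital admission. Resupply every six months would fall near Day 365, inside the window, and if the drug is shipped the coordinator contacts the patient. That contact is required to cover only receipt and damage, so it does not replace the missing check.

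Nor does all stroke ascertainment rest on recall. C.3.a has a physician review the patient and the medical records for stroke at the study visits, with the neuroradiology readings available. That should date events that reached care. What remains is mainly TIAs for which no care was sought. D.2 does not expect a significant reduction in recurrent stroke in this study.

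Finally, a reader might extend the point to the investigator alert in E.9, because E.3 and E.4 do not name the coordinating centre as a recipient of reports. That is a matter of unstated detail: events go into REDCap, monitors review them (E.11), and E.7 has the sponsor weigh causality. It does not follow from the contact schedule and is not part of this point.

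These objections lower the severity. They leave the mismatch between B.9 and Figure 1 in place.

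**Conclusion.** The inconsistency is real and of low severity. Figure 1 leaves 160 days without a scheduled check where B.9 allows about 122, and the conclusion holds at any ordinary month length. The consequence is limited to late detection of events that patients do not volunteer and to dating of TIAs outside medical care. The 7% figure rests on even spread of events and on their surfacing only at scheduled contacts. How many events are of that kind is unknown, so it is a share of such events and not of all events. The primary endpoints come from MRI at baseline and week 78, so they and the power calculation are untouched.

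**What to change.** In Figure 1, add a Day 400 contact with the same rows as Day 320: history and current medications, stroke adjudication, adverse events and serious adverse events. This continues the 80-day step (320, 400, 480), leaves B.9 as written and brings the longest interval to 80 days. The cost is one column and at most 150 coordinator contacts. If the 25–30% withdrawal assumed in D.3 has all occurred by then, the number is 150 × 0.70 = 105 to 150 × 0.75 = 112.5, or about 105 to 113. The contact could be combined with a shipment-receipt call if one falls near that date.

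If no extra contact is wanted, move Day 480 to about Day 430. Both remaining intervals (110 and 116 days) then fall within four months at no added cost, but the longest stays well above 80 days and the mean wait improves less (42 days against 35).
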